## LIST OF ABBREVIATIONS AND DEFINITIONS OF TERMS

Abbreviation or Term	Description
AE	adverse event
BRAF V600	V600 codon of the BRAF oncogene
CI	confidence interval
CNS	central nervous system
COVID	Coronavirus Disease
CR	complete response
CRF	case report form
DCR	disease control rate
DoR	duration of response
ECOG	Eastern Cooperative Oncology Group
eCRF	electronic Case Report Form
EORTC	European Organization for the Research and Treatment of Cancer
GHS	Global Health Status
HRQoL	health-related quality of life
IMC	Internal Monitoring Committee
iRANO	immunotherapy Response Assessment for Neuro-Oncology
IV	intravenous (ly)
IRC	independent review committee
LDH	Lactic Acid Dehydrogenase
LPI	last patient in (last patient enrolled)
MedDRA	Medical Dictionary for Regulatory Activities
MRI	magnetic resonance imaging
NCI CTCAE	National Cancer Institute Common Terminology Criteria for Adverse Events
NA	not applicable
ORR	objective response rate
OS	overall survival
PD	progressive disease
PD-L1	programmed death ligand 1
PFS	progression free survival
PR	partial response
PRO	patient-reported outcome
PT	Preferred Term
QLQ-C30	Quality-of-Life Questionnaire Core 30

QLQ-BN20	Quality-of-Life Questionnaire - Brain Cancer Module
RECIST	Response Evaluation Criteria in Solid Tumors
SAE	serious adverse event
SAP	statistical analysis plan
SD	stable disease
SLD	sum of longest diameter
SOC	System Organ Class
SRT	stereotactic radiotherapy
TEAE	treatment-emergent adverse event
TTD	time to deterioration
ULN	upper limit of normal

## 1. **INTRODUCTION**

This Statistical Analysis Plan (SAP) provides details of the planned analyses and statistical methods for Study MO39136 (TRICOTEL): A Phase II, two cohort study evaluating the safety and efficacy of cobimetinib plus atezolizumab in BRAFV600 wild-type melanoma with central nervous system metastases and cobimetinib plus atezolizumab and vemurafenib in BRAFV600 mutation positive melanoma with central nervous system metastases. The background for the study can be found in the study protocol.

### 1.1 **OBJECTIVES AND ENDPOINTS**

This study will evaluate the efficacy and safety of cobimetinib plus atezolizumab in patients with BRAFV600 wild-type melanoma with central nervous system (CNS) metastases and of cobimetinib plus atezolizumab and vemurafenib in BRAFV600 mutation-positive melanoma patients with CNS metastases. Specific objectives and corresponding endpoints for the study are outlined [Table 1](#) below.

**Table 1 Objectives and Corresponding Endpoints**

Primary Efficacy Objectives	Corresponding Endpoints

To evaluate intracranial ORR with cobimetinib plus atezolizumab in BRAFV600 wild-type melanoma as assessed by an IRC

To evaluate intracranial ORR with cobimetinib plus atezolizumab and vemurafenib in BRAFV600 mutation-positive melanoma as assessed by an IRC

	

Intracranial ORR defined as the proportion of patients with either a CR or PR in their intracranial disease based on two consecutive assessments <math>\geq 4</math> weeks apart. Disease status for this endpoint will be determined by an IRC in accordance with RECIST v1.1 with modified measurability definition for intracranial lesions (<math>\geq 0.5</math> cm by MRI) and allowing up to five intracranial target lesions

Secondary Efficacy Objectives	Corresponding Endpoints

To evaluate the efficacy of cobimetinib plus atezolizumab in BRAFV600 wild-type melanoma with CNS metastases

To evaluate the efficacy of cobimetinib plus atezolizumab and vemurafenib in BRAFV600 mutation-positive melanoma with CNS metastases

	

Extracranial ORR, defined as the proportion of patients with either a CR or PR in their extracranial disease based on two consecutive assessments <math>\geq 4</math> weeks apart, as determined by the investigator according to RECIST v1.1

Overall ORR, defined as the proportion of patients with either a CR or PR in their overall disease (i.e., including intracranial and extracranial disease) based on two consecutive assessments <math>\geq 4</math> weeks

**Table 1 Objectives and Corresponding Endpoints (cont.)**

Secondary Efficacy Objectives	Corresponding Endpoints
	
apart, as determined by the investigator according to RECIST v1.1
 
 
• Intracranial, extracranial, and overall PFS defined as the time from study treatment initiation to the first occurrence of disease progression or death from any cause, whichever occurs first, as determined by the investigator according to RECIST v1.1
 
• Intracranial, extracranial, and overall DOR, defined as the time from the first occurrence of a documented objective response based on two consecutive assessments <math>\geq 4</math> weeks apart to disease progression or death from any cause (whichever occurs first), as determined by the investigator according to RECIST v1.1
 
• Intracranial, extracranial, and overall DCR, defined as the proportion of patients with a CR or PR or SD at 16 weeks from study treatment initiation, as determined by the investigator according to RECIST v1.1
 
• OS defined as the time from study treatment initiation to death from any cause
 
• Time from study treatment initiation to cognitive symptom deterioration, defined as a change (<math>\geq 10</math> points on a 0-100 scale) on selected scales of the EORTC-BN20 (visual disorder, motor dysfunction, communication deficit, headaches, seizures and drowsiness)
 
• Time from study treatment initiation to symptom and function deterioration defined as a change (<math>\geq 10</math> points on a 0-100 scale) in fatigue, physical functioning, cognitive functioning, or role functioning as measured by the Fatigue, Physical, Cognitive, Role Functioning scales of the EORTC QLQ-C30
 
• Duration of Stable/Improved HRQoL scores as assessed through use of the two-item GHS/QoL subscale (Questions 29 and 30) of the EORTC QLQ-C30
 

**Table 1 Objectives and Corresponding Endpoints (cont.)**

Exploratory Efficacy Objective(s)	Corresponding Endpoints

 
• To evaluate the efficacy of cobimetinib plus atezolizumab in BRAFV600 wild-type melanoma with CNS metastases
 
• To evaluate the efficacy of cobimetinib plus atezolizumab and vemurafenib in BRAFV600 mutation-positive melanoma with CNS metastases
 
	
 
• Intracranial ORR defined as the proportion of patients with either a CR or PR in their intracranial disease based on two consecutive assessments <math>\geq 4</math> weeks apart. Disease status for this endpoint will be determined by the investigator according to iRANO criteria.
 
• ORR in intracranial, extracranial, and overall disease as determined by investigator according to immune-modified RECIST with modified measurability definition for intracranial lesions (<math>\geq 0.5</math> cm by MRI) and allowing up to five intracranial target lesions
 
• Intracranial, extracranial, and overall PFS as determined by the investigator according to immune-modified RECIST
 
• Intracranial, extracranial, and overall DOR as determined by the investigator according to immune-modified RECIST
 
• Radiotherapy-assisted PFS defined as time from study treatment initiation to the first occurrence of disease progression or death from any cause, whichever occurs first, as determined by the investigator according to RECIST v1.1 modified by excluding <math>\leq 3</math> lesions that can be treated by SRT from the sum of largest diameters from baseline onwards
 
• Timing of increase or change in corticosteroid use during treatment
 
• Time from study treatment initiation to subsequent intracranial and systemic anti-cancer treatment
 
• Change from baseline scores over time in treatment/disease-related symptoms as evaluated by the EORTC QLQ-C30 and QLQ-BN20 questionnaires
 

**Table 1 Objectives and Corresponding Endpoints (cont.)**

Safety Objective(s)	Corresponding Endpoints

 
To evaluate the safety of cobimetinib plus atezolizumab in BRAFV600 wild-type melanoma with CNS metastases
 
To evaluate the safety of cobimetinib plus atezolizumab and vemurafenib in BRAFV600 mutation-positive melanoma with CNS metastases
 
	
 
Occurrence and severity of adverse events, with severity determined according to NCI CTCAE v4.0
 
Change from baseline in targeted vital signs
 
Change from baseline in targeted clinical laboratory test results
 

Exploratory Biomarker Objective(s)	Corresponding Endpoints

 
To perform molecular characterization of melanoma disease in plasma and tumour tissue
 
	
 
Relationship between biomarkers (including, but not limited to; PD-L1, BRAF and NRAS) in plasma and tumour tissue and clinical efficacy parameters
 

CR=complete response; DCR=disease control rate; DOR=duration of response; EORTC QLQ-C30 and QLQ-BN20=European Organization for Research and Treatment of Cancer Quality of Life questionnaire core questionnaire and brain cancer specific module; GHS=Global Health Status; HRQoL=health-related quality of life; MRI=magnetic resonance imaging; iRANO=immunotherapy Response Assessment for Neuro-Oncology; IRC=Independent Review Committee; NCI CTCAE=National Cancer Institute Common Terminology Criteria for Adverse Events; ORR=objective response rate; OS=overall survival; PFS=progression-free survival; PR=partial response; PD-L1=programmed death ligand 1; PRO=patient-reported outcome; RECIST v1.1=Response Evaluation Criteria in Solid Tumors version 1.1; SD=stable disease; SRT=stereotactic radiotherapy.

## 1.2 STUDY DESIGN

Study MO39136 is a Phase II, two cohort, efficacy and safety study of BRAFV600 status-specific combination treatment with cobimetinib, atezolizumab and vemurafenib for melanoma with CNS metastases. Study patients will be assigned to a study treatment cohort based on locally determined BRAFV600 disease status:

- Cohort 1: Patients with BRAFV600 wild-type disease will be assigned to treatment with cobimetinib plus atezolizumab in Cohort 1.
- Cohort 2: Patients with BRAFV600 mutation-positive disease will be assigned to treatment with cobimetinib plus atezolizumab and vemurafenib in Cohort 2.

The study includes assessment of patient reported quality of life outcomes as well as exploratory biomarker evaluations.

Study treatment will consist of:

- Cohort 1: orally administered cobimetinib and intravenously (IV) administered atezolizumab in 28-day cycles.

- Cohort 2: orally administered cobimetinib and vemurafenib for an initial 28-day treatment run-in period, followed by cobimetinib, vemurafenib and IV atezolizumab for subsequent 28-day cycles.

Disease status for the purposes of treatment decisions will be determined by the investigator. Study treatment for all patients in both cohorts will be continued until investigator-determined disease progression according to Response Evaluation Criteria in Solid Tumors version 1.1 (RECIST v1.1) (with two exceptions as described below), death, unacceptable toxicity, withdrawal of consent, or pregnancy, whichever occurs first.

Study treatment may be continued beyond progression per RECIST v1.1 if:

[figure not shown]
- pseudoprogression due to the effects of immunotherapy is suspected to have occurred or disease progression is limited to  $\leq 3$  intracranial lesions that can be controlled with stereotactic radiotherapy (SRT).
- Patient is clinically stable, have a favourable benefit-risk ratio (all the criteria listed in the protocol have to be met).

The disease status of patients who continued study treatment and underwent intracranial SRT will be determined by the investigator according to RECIST v1.1 modified by excluding any treated lesions from the sum of largest diameters from baseline onwards.

Patients will attend a Study Treatment Discontinuation Visit within  $28 \pm 7$  days of their last study treatment dose. All AEs will be reported until 30 days after the last study treatment dose. After the Study Treatment Discontinuation Visit, patients who have not yet progressed will be followed every 8 or 12 weeks for disease status until disease progression has been confirmed, and all patients will be followed every three months for survival and new anti-cancer treatments.

Figure 1 presents an overview of the study design.

**Figure 1 Study Schema**

- a. Documented BRAFV600 status in melanoma tumour tissue
- b. Treatment regimen begins with a 28-day run-in period with vemurafenib and cobimetinib only.
- c. Clinically stable patients who have a favorable benefit-risk ratio as defined in the protocol may continue study treatment following radiographic progression per RECIST v1.1 with Medical Monitor approval.

BRAFV600 = V600 codon of the BRAF oncogene; N = number of patients

Efficacy will be assessed in intracranial disease alone (primary efficacy endpoint) as well as in extracranial and overall (both intracranial and extracranial) disease (secondary and exploratory efficacy endpoints). Disease status will be determined according to RECIST v1.1 with a modified measurability definition for intracranial lesions ( $\geq 0.5$  cm by magnetic resonance imaging [MRI]) and allowing up to five intracranial target lesions (in addition to any extracranial target lesions). Exploratory analyses of disease status will include evaluations by immune-modified RECIST, RECIST v1.1 modified by excluding any SRT-treated lesions from the sum of largest diameters from baseline onwards (if applicable), and immunotherapy Response Assessment for Neuro-Oncology (iRANO) criteria. Disease status for the primary endpoint will be determined by an Independent Review Committee (IRC). All other efficacy endpoints will be analysed according to investigator disease status determinations. Disease responses for all endpoints will be confirmed by two consecutive assessments at least four weeks apart. Regardless of whether patients continue treatment beyond disease progression per RECIST v1.1, tumour assessments must be repeated approximately four weeks later (or sooner if necessary e.g., due to clinical progression).

Approximately 60 patients will be enrolled into each treatment cohort for a total of 120 patients enrolled. With an estimated study drop-out rate of 15%, approximately 50 patients in each cohort are expected to be evaluable for the primary efficacy endpoint. To ensure approximately equal sample sizes in each treatment cohort, study eligibility and screening may be adjusted with respect to BRAFV600 status once enrolment reaches 60 patients in either treatment cohort.

Based on the results of the primary analysis for Study CO39722 (IMspire170) of cobimetinib plus atezolizumab combination in previously untreated advanced BRAFV600 wild-type melanoma patients (see Section 1.3.2.4 of the study protocol), enrollment in the BRAFV600 wild-type cohort has been discontinued. Ongoing patients in this cohort may continue study treatment as per protocol, according to investigator's medical judgement.

### **1.2.1 Treatment Assignment**

Study patients will be assigned to study treatment cohort based on locally determined BRAFV600 disease status. Patients with BRAFV600 wild-type disease will be assigned to treatment with cobimetinib plus atezolizumab in Cohort 1. Patients with BRAFV600 mutation-positive disease will be assigned to treatment with cobimetinib plus atezolizumab and vemurafenib in Cohort 2.

### **1.2.2 Independent Review Facility**

Disease status for the primary endpoint will be determined by an IRC. IRC membership and procedures will be described in the IRC charter.

### **1.2.3 Data Monitoring**

The Internal Monitoring Committee (IMC) will monitor patient safety throughout the study and will assess the benefit-risk, as described in the IMC charter. The IMC will include Sponsor representatives from Clinical Science, Drug Safety, and Biostatistics. In addition to the ongoing assessment of the incidence and nature of AEs (particularly Grade 3 events), serious adverse events (SAEs), deaths, and laboratory abnormalities performed by the investigator and the Medical Monitor, the IMC will review cumulative data at regular intervals throughout the conduct of the study and assess the benefit-risk.

At the time of each review, the IMC will make appropriate recommendations (e.g., the study should continue as planned, additional analyses should be performed, enrolment should be held pending further safety evaluations). Decisions will be made in consideration of the totality of the available data. Ad hoc meetings may be called in addition to scheduled meetings, as necessary, to provide recommendations on management of any potential new safety signals. Specific operational details such as the committee's composition, frequency and timing of meetings, members' roles and responsibilities, and data to be reviewed are described in the IMC charter.

## **2. STATISTICAL HYPOTHESES**

There is no formal statistical study hypothesis. All statistical analyses will be entirely descriptive.

## **3. SAMPLE SIZE DETERMINATION**

The purpose of this Phase II study is estimation and hypothesis generation regarding the effect of cobimetinib plus atezolizumab on CNS metastases from BRAFV600 wild-type

melanoma and the effect of cobimetinib plus atezolizumab and vemurafenib on CNS metastases from BRAFV600 mutation-positive melanoma. There are no reference data available on the use of these combination therapies in these patient populations.

There is no formal statistical hypothesis in this study. The planned total sample size of approximately 120 patients (60 patients/cohort) is based on based on an estimated study drop-out rate of 15%, the primary endpoint and 95% confidence intervals (CIs) for each treatment regimen. If necessary, study eligibility and screening may be adjusted with respect to BRAFV600 status once enrolment reaches 60 patients in either treatment cohort. No power calculation has been performed.

Point estimates and 95% CIs for a range of possible outcomes produced using nQuery (Version 7) with 100 evaluable patients (50 per treatment cohort) are provided in [Table 2](#).

**Table 2 Objective Response Rate Estimates and Confidence Intervals with 50 Evaluable Patients per Treatment Cohort**

Intracranial Response Rate in Each Cohort	95% Confidence Interval
35%	(21.8%, 48.2%)
40%	(26.4%, 53.6%)
45%	(31.2%, 58.8%)
50%	(36.1%, 63.9%)
55%	(41.2%, 68.8%)

#### 4. ANALYSIS SETS

The following populations are defined:

Population	Definition
Safety-evaluable Population	All participants received at least one dose of study treatment (e.g., atezolizumab, cobimetinib, or vemurafenib)
Evaluable Population	All enrolled patients who received study medication and have at least two post-baseline intracranial tumour assessments for response evaluation
PRO-evaluable Population	All patients who received any amount of any study medication (e.g., atezolizumab, cobimetinib, or vemurafenib) and have a baseline and at least one post baseline PRO assessment in the questionnaire of interest (EORTC QLQ-C30 or EORTC QLQ-BN20)

EORTC QLQ-C30 and QLQ-BN20=European Organization for Research and Treatment of Cancer Quality of Life questionnaire core questionnaire and brain cancer specific module; PRO=patient-reported outcome.

## **5. STATISTICAL ANALYSES**

### **5.1 GENERAL CONSIDERATION**

A primary study analysis that includes analyses of all efficacy endpoints and safety summaries will be conducted based on data collected up to 6 months after the last patient is enrolled in the study (last patient in [LPI]). The final study analysis including updated analyses of safety and efficacy endpoints will be conducted based on data collected up to 24 months after LPI.

Unless otherwise indicated, efficacy analyses will be based upon the Evaluable population in each cohort consisting of all enrolled patients who received study medication and have at least two post-baseline tumour assessments for response evaluation. Analyses of safety, survival, corticosteroid use, and time to subsequent intracranial or systemic anti-cancer treatment endpoints will be conducted based upon the Safety evaluable population in each cohort consisting of all patients who received at least one dose of study medication. Analyses of patient-reported outcome (PRO) endpoints will be conducted based upon the PRO-evaluable population.

Any incomplete or missing death date will be handled separately for safety and efficacy analyses. In safety analyses, all deaths will be included, regardless of completeness of death date; patients who died with a partial or missing death date will be included as an event. In efficacy analyses, a death is considered an event only if a complete death date is available; patients who died with only a partial or missing death date will not be considered as a death event.

Based on the results of the primary analysis for Study CO39722 (IMspire170) of cobimetinib plus atezolizumab combination in previously untreated advanced BRAFV600 wild-type melanoma patients (see Section 1.3.2.4 of the study protocol), enrollment in the BRAFV600 wild-type cohort was discontinued. The primary endpoint will not be evaluated on Cohort 1. Only a subset of analysis on efficacy secondary endpoints will be performed.

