6.4.1 Primary Efficacy Endpoint

The primary efficacy objective is to evaluate the intracranial ORR in the BRAF^{V600} mutation-positive study cohort. Intracranial ORR is defined as the proportion of patients with a complete or partial response in their intracranial disease based on two consecutive assessments ≥ 4 weeks apart. Disease status will be determined by an IRC according to RECIST v1.1 with a modified measurability definition for intracranial lesions (≥ 0.5 cm by MRI) and allowing up to five intracranial target lesions. Data for patients with no post-baseline intracranial tumour assessment will be excluded from efficacy analyses. For intracranial response rate, a 95% Pearson-Clopper CI will be calculated and presented.

A sensitivity analysis of the primary endpoint that includes patients with unconfirmed CR or PR will also be conducted in each cohort based upon the Safety population in order to detect a potential bias with regard to the primary analysis.

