## **STATISTICAL ANALYSIS PLAN AMENDMENT RATIONALE**

Key changes to the SAP, along with the rationales for each change, are summarized below.

Section	Description of Change	Rationale for Change
4	Patient-reported outcome (PRO)-evaluable population added for the PRO analysis	It is stated in the protocol that “Only patients with a non-missing baseline assessment and at least one non-missing post-baseline assessment will be included in PRO analyses.” For clarify purpose, we added PRO population in the Section 4 and clarified that this population will be used for PRO analysis to ensure compliance with the protocol.
5.1	Only a subset of efficacy analysis will be done on Cohort 1	Given that the recruitment of Cohort 1 was stopped prematurely, it is no longer appropriate to produce all the efficacy analysis due to small sample size. Thus, the Statistical Analysis Plan is updated to limit the efficacy analysis.
5.3.1	No analysis on primary endpoint on Cohort 1	After the premature discontinuation of Cohort 1, it was decided to not perform the independent review of scan for patients in Cohort 1. Thus, all analyses on the primary endpoint will be performed on Cohort 2 only.
5.3.3	Adding sensitivity analysis of primary endpoints on all treated patients (safety population)	The analysis on primary endpoint is planned on evaluable population only, which excludes subjects with less than 2 scans. Excluding these subjects could lead to an inflation of the response rate by excluding the early progression or death. Therefore, we add an analysis on all treated patients to assess the bias introduced by excluding these patients.
5.3.4.1	New subgroup	Additional subgroup added to better explore the effect of demographic characteristics and clinical and biological prognostic factors on the efficacy endpoint.
5.4	Adding analysis secondary efficacy endpoints on all treated patients (safety population)	The analysis on efficacy endpoint (objective response rate [ORR], progression-free survival [PFS], and disease control rate [DCR]) are planned on evaluable population, which excludes subjects with less than 2 scans. Excluding these subjects could lead to an inflation of the response rate by excluding the early progression or death. Therefore, we add an analysis on all treated patients to assess the bias introduced by excluding these patients.

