## **5.4 SECONDARY ENDPOINTS ANALYSES**

Unless otherwise noted, all efficacy analyses will be performed on both the evaluable patient population and all treated patients (safety population).

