#### **5.4.2.4 Intracranial, Extracranial and Overall Progression-Free Survival – RECIST**

Intracranial, extracranial, and overall progression-free survival (PFS) are defined as the time from study treatment initiation to the first occurrence of disease progression, as

determined by the investigator according to RECIST v1.1, or death from any cause, whichever occurs first. Data for patients who have not experienced disease progression or death at the time of analysis data cutoff will be censored at the last evaluable tumor assessment date.

Kaplan-Meier methodology will be used to estimate median intracranial, extracranial, and overall PFS. Kaplan-Meier curves will be provided. The 95% CI of the median PFS will be constructed using the Brookmeyer and Crowley method (Brookmeyer and Crowley 1982).

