#### **5.4.2.7 Overall Survival**

The overall survival (OS) analysis will be based on the safety population (all treated patients) only.

OS is defined as the time from study treatment initiation to death from any cause. For patients who are alive at the time of analysis data cutoff, OS time will be censored at the date the patient was last known to be alive.

Kaplan-Meier methodology will be used to estimate OS. Kaplan-Meier curves will be provided. The 95% CI of the median OS will be constructed using the Brookmeyer and Crowley method.

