#### **5.5.1.8 DoR, DCR and PFS by IRC – RECIST**

Intracranial PFS, DoR, and DCR, as determined by the IRC according to RECIST v1.1, will be analyzed using the same methods described for intracranial PFS, DoR, and DCR determined by investigator on all patients who received at least one dose of study medication (safety evaluable population).

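### Immune-modified RECIST PFS and radiotherapy-assisted PFS default to a population that requires two post-baseline brain scans, so early deaths drop out of curves timed from first dose

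*SAP*

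**What the plan says.** SAP 5.1 sets the default: "Unless otherwise indicated, efficacy analyses will be based upon the Evaluable population in each cohort". SAP 4 defines that population as "All enrolled patients who received study medication and have at least two post-baseline intracranial tumour assessments for response evaluation". SAP 5.4.2.4 defines PFS as "time from study treatment initiation to the first occurrence of disease progression" or death from any cause.

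Several analyses depart from the default:

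- **Secondary endpoints.** SAP 5.4 states, with a proviso for exceptions, that "all efficacy analyses will be performed on both the evaluable patient population and all treated patients (safety population"). The amendment rationale for this change names ORR, PFS and DCR. It says that leaving out patients with fewer than two scans can inflate results by losing early progression or death, and concludes: "Therefore, we add an analysis on all treated patients to assess the bias introduced by excluding these patients".
- **Overall survival (5.4.2.7).** "The overall survival (OS) analysis will be based on the safety population (all treated patients) only".
- **IRC intracranial PFS (5.5.1.8, exploratory).** Run "on all patients who received at least one dose of study medication (safety evaluable population").

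Immune-modified RECIST PFS (5.5.1.3) and radiotherapy-assisted PFS (5.5.1.5) refer back to 5.4.2.4 for methods and name no population.

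Protocol 6.4.1, in the paragraph on the primary response endpoint, adds: "Data for patients with no post-baseline intracranial tumour assessment will be excluded from efficacy analyses".

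**The concern.** Membership of the Evaluable population is decided by what happens after time zero. A patient must stay alive and in follow-up long enough for two brain scans, yet the PFS clock starts at first dose. No member can die before the second scan. A treated patient who dies at week 6 has a PFS event by definition but is absent from the curve. So is a patient who deteriorates and withdraws before the second scan. The early part of the curve is partly immortal time, and the whole curve is lifted.

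The SAP's authors recognised this for the secondary endpoints and added all-treated analyses. That repair was not carried to 5.5.1.3 and 5.5.1.5. These two curves invite comparison with standard RECIST PFS, because they ask whether allowing for pseudoprogression or for stereotactic radiotherapy lengthens PFS. Set beside an all-treated RECIST curve, evaluable-only versions could look better through patient selection alone.

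**Working it through.** **1. The plan's own figure.** Inputs (SAP 1.2, and protocol 3.1 for the mutation-positive cohort): 60 enrolled, 15% drop-out, about 50 evaluable. Check: 50 / 0.85 = 58.8, so 59 needed against 60 planned; 60 × 0.85 = 51 against 50. The figures agree to within rounding. The documents state no expected PFS.

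**2. When the second scan falls.** Protocol Appendix 2 puts the first post-baseline scan in the last week of Cycle 2 (2 × 28 days = 8 weeks), then every 8 weeks, so the second scheduled scan is at about week 16. Protocol 4.5.6 requires progression to be re-scanned about four weeks later, so a patient progressing at week 8 can have a second scan at about week 12.

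**3. Which population governs 5.5.1.3 and 5.5.1.5.** The both-populations sentence stands at the head of 5.4, the secondary-endpoint section; these two analyses are in 5.5. The SAP's other cross-references to the PFS method show how it uses them:

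- PRO time to deterioration (5.4.2.8): same method, population named (PRO-evaluable).
- Corticosteroid timing (5.5.1.6): same methods, population named (safety).
- Time to subsequent treatment (5.5.1.7): same methods, population named (safety).
- IRC intracranial PFS (5.5.1.8): same methods as the investigator version, population named (safety-evaluable).
- Immune-modified RECIST PFS (5.5.1.3) and radiotherapy-assisted PFS (5.5.1.5): same methods, no population named.

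Elsewhere, then, a reference to methods does not settle the analysis set. With none stated, the 5.1 default applies.

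**4. Size.** Let k of the 10 excluded patients have a PFS event before the second scan, and treat the other 10 − k as uninformative losses. After the second scan:

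S_all(t) = S_eval(t) × (1 − k/60), so the overstatement factor is 1 / (1 − k/60).

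- k = 0: factor 1.00, no bias.
- k = 5: 1 − 5/60 = 0.917, factor 1.09. If the five uninformative patients leave the denominator altogether, 55/50 = 1.10.
- k = 10: 1 − 10/60 = 0.833, factor 60/50 = 1.20.

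For scale, take evaluable-set 6-month PFS of 29%, 46% and 60%. Protocol 1.1 reports 29% and 46%, and a rate above 60%, for other regimens in melanoma brain metastases; they are illustrations, not predictions.

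| Evaluable-set PFS | All-treated, k = 5 | All-treated, k = 10 |
|---|---|---|
| 29% | 26.6% | 24.2% |
| 46% | 42.2% | 38.3% |
| 60% | 55.0% | 50.0% |

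The all-treated median falls where the evaluable curve reads 0.5 / 0.917 = 54.5% (k = 5) or 0.5 / 0.833 = 60% (k = 10).

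**5. Simulation check.** Assumed inputs: median time to progression 18, 26 or 35 weeks, median time to death 35 or 52 weeks, 10% withdrawal per year, second scan at week 12 or 16. Between 16.8% and 29.5% of patients were excluded, and 26-week PFS was overstated by 4.9 to 14.0 points. The scenarios closest to the planned exclusion (10/60 = 16.7%) had median time to death of 52 weeks and a second scan at week 12: 16.8% excluded, 26-week PFS overstated by 4.9 to 7.6 points. For example, 0.438 against 0.373 is a factor of 1.17. The formula gives the same: survival to week 12 is 0.5^(12/52) = 0.852, and 1/0.852 = 1.17. Most exclusions here are deaths by construction, so this confirms the mechanism but says nothing about the true split.

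**The case against.** The strongest reply is that the SAP's authors found this problem and dealt with it. Secondary investigator PFS (intracranial, extracranial and overall) is run on all treated patients for the stated purpose of assessing the bias, and IRC intracranial PFS is all-treated. That stands. A reader might infer that every PFS curve is affected with nothing beside it, or that no exploratory PFS covers all treated patients; 5.4 and 5.5.1.8 rule out both. Nor is the comparison of IRC with investigator intracranial PFS necessarily confounded by population, since both exist on all treated patients.

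A second reply is that sharing the methods of 5.4.2.4 could carry over both populations. This is arguable, but the SAP's usage elsewhere points the other way, and two programmers could produce different curves from the same text.

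Third, the bias has limits. Patients who progress at week 8 stay in the set if the required re-scan is done, and uninformative withdrawals do not bias a Kaplan-Meier estimate. Both stand. The re-scan is only a partial safeguard, because protocol 4.5.6 ends scheduled assessments once a new anti-cancer treatment starts.

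Fourth, the protocol 6.4.1 exclusion sits in the primary-endpoint paragraph. A reader might infer that it removes pre-scan deaths from the all-treated PFS too. That would defeat the stated purpose of the all-treated analysis, and the SAP does not repeat the sentence. But its wording is not limited to response, and SAP Appendix 1 does not address it, so a clarification is warranted.

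Finally, the evaluable set is the protocol's default for efficacy (section 6). Deleting evaluable-set PFS would be a preference; keeping it as a labelled supplement shows the selection effect.

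**Conclusion.** The concern holds for immune-modified RECIST PFS and radiotherapy-assisted PFS. Both start at first dose and, on the SAP's default, use a population that must reach a second scan at about week 12 to 16, so earlier deaths cannot appear. The amendment rationale acknowledges the same bias for the secondary endpoints. For secondary PFS the all-treated curve exists, and what is missing is a statement of which curve leads.

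At 60 treated and 50 evaluable, the overstatement after the second scan runs from none to a factor of 1.20, with about 1.09 if half the excluded patients had early events. At an evaluable-set PFS of 60% that is 0, 5 or 10 percentage points. The split among the 10 is an assumption, so the documents do not support a firm statement that PFS will be overstated by a given amount. What they do support is the direction if any excluded patient had an early event. The endpoints are secondary or exploratory and the study is descriptive, which limits the consequence but does not remove the reason to correct the rule.

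**What to change.** 1. **SAP 5.5.1.3 and 5.5.1.5:** state that PFS is analysed on the safety-evaluable population, as 5.4.2.7 does for OS and 5.5.1.8 for IRC PFS.
2. **SAP 5.4.2.4:** make the all-treated PFS the lead result and keep the evaluable-set PFS as a labelled supplementary analysis.
3. **SAP Appendix 1:** state that the protocol 6.4.1 exclusion of patients without a post-baseline intracranial assessment applies only to the evaluable-population response analysis, so that a death before the first scan counts as an event in the all-treated PFS.

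The cost is SAP wording. No new data are needed, and the third item is placed in the SAP so that the protocol text can stay as it is. The downside is that reported PFS may be somewhat less favourable.
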